2 OBJECTIVES

The overall objective is to determine the extent to which activating patients to address health-related financial burdens that impact treatment adherence and unmet SDHs improves disease control, and the mechanisms through which primary and secondary outcomes are achieved. The specific aims of the study are listed below.

Aim 1: Determine the effectiveness of CareAvenue relative to usual care in improving glycemic control and patient-centered outcomes such as CRN behaviors and perceived financial burdens. We hypothesize that participants randomized to CareAvenue will have a change in HbA1c (**primary outcome**) compared to usual care. We will measure the change in HbA1c at baseline, 6 months (-2 weeks/+4 weeks), and 12 months (-2 weeks/+4 weeks) using an HbA1c machine. Additionally, we hypothesize that other patient-centered outcomes (**secondary outcomes**) will change compared to usual care. Secondary outcomes will be measured at baseline, 6 months (-2 weeks/+4 weeks), and 12 months (-2 weeks/+4 weeks). They include blood pressure (measured with an automated blood pressure cuff), Cost-related non-adherence behaviors with prescribed treatment regimens related to diabetes, Cost-related non-adherence behaviors with prescribed treatment regimens related to other conditions being managed, Perceived financial burden, and unmet social risk factors.

Aim 2: Examine mediators and moderators of the effectiveness of CareAvenue on primary and secondary outcomes. We hypothesize that the intervention will significantly improve skills and self-efficacy in uptake and use of resources leading to decreased financial burdens, perceived stress of unmet SDHs, and improved adherence to treatment regimens, with these changes being the primary mechanism through which improvements in glycemic control are achieved. We also hypothesize that CareAvenue will be most effective among patients with high need for resources and low self-efficacy in navigating resources at baseline.

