6 STUDY DESIGN AND PROCEDURES

6.1 Experimental Design and Randomization

We will test our hypotheses using a two arm-randomized control trial. In exploratory analyses, we will examine individual differences in response to treatment. We will collect outcome data at 3 time points: baseline, and 6 (-2 weeks/+4 weeks) and 12 months (-2 weeks/+4 weeks) after initial engagement with CareAvenue. Data collectors and analysts will be blind to the study hypotheses, and analysts will be further blinded by which group participants are allocated to.

Participants will be randomized to either usual care or the intervention group receiving CareAvenue. Usual care is defined as existing practices for addressing patients' financial burden and non-medical issues in the clinic flow. We will provide all control group participants with contact information for the Guest Assistance Program (GAP) at the University of Michigan Health System (UMHS). GAP provides assistance with medical and non-medical needs and resources to patients receiving medical care at UMHS. It consists of social workers who work with clients to help them access a variety of resources. Providing contact information for GAP to the control arm will ensure another layer of blinding of the intervention, and provides an opportunity to assess the benefits of an autonomy supportive, multi-component skills-training intervention on outcomes.

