8.2 Regression models

For the primary outcome (HbA1c), we will fit a longitudinal mixed-effects model to all repeated measurements during the pre-randomization baseline period and the one-year intervention period. The model will have the intervention (yes/no) as the main independent

variable and HbA1c accounted for as a repeated measure within patients. Thus, we will model HbA1c as a function of fixed effects for the treatment arm (the intervention group vs. the control group), the observation period (baseline vs. one-year intervention period), and a treatment-by-time period interaction term, with adjustment for confounding covariates (age, gender, race, income, health insurance type, comorbidities, health literacy). For this model, the coefficient of the treatment-by-time period interaction effect estimates the key parameter of interest: changes in HbA1c levels. Random effects are included in the model to adjust for HbA1c variation over time within patients. We will take a similar modeling approach to secondary outcome measures (CRN behaviors, perceived financial burdens, perceived stress of unmet SDHs). We will also dichotomize outcomes based on standard thresholds (eg., baseline HbA1c 8-9% vs > 9%) and use similar mixed-effects logistic regression models to test differences in HbA1c, CRN behaviors, perceived financial burdens, and perceived stress of unmet SDHs across treatment arms.

Among those randomized to CareAvenue in Aim 1, we will assess the change in magnitude of the outcome coefficient's association with the intervention before and after the adjustment of mediators of interest (see Figure 1, conceptual model). We will examine the Lagrange Multiplier and Wald Tests to consider the deletion or inclusion of paths based on our hypotheses.⁵⁶ Once the model is identified, we will test for group differences (i.e. intervention vs. control) in latent constructs and in the paths between these constructs. This method will allow us to estimate the intervention effects on the constructs directly as well as their relationships to one another.⁵⁶ We will follow guidelines for adequate reporting of SEM using three goodness-of-fit indices: Bentler-Bonnet's Normed Fit Index (NFI), Bentler-Bonnet's Non-Normed Fit Index (NNFI), and the Comparative Fit Index (CFI). We will also verify the root mean-square error of approximation (RMSEA) as an index of misfit. Well-fitting models will have fit indices of .90 or higher and <.06 for RMSEA.

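### Aim 2 mediation: data-driven tests may change the paths before inference, with no stated safeguard, so results for data-selected paths, weak ones above all, are unreliable

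*Combined protocol and SAP*

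**What the plan says.** Section 2 gives Aim 2 a directional hypothesis. The intervention should improve skills and self-efficacy, ease burden and stress, and improve adherence, "with these changes being the primary mechanism through which improvements in glycemic control are achieved".

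Section 8.2 sets out the analysis in this order:

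- It starts from named mediators: "adjustment of mediators of interest (see Figure 1, conceptual model").
- It allows the model to change: "We will examine the Lagrange Multiplier and Wald Tests to consider the deletion or inclusion of paths based on our hypotheses".
- It then tests the arms: "Once the model is identified, we will test for group differences (i.e. intervention vs. control) in latent constructs", and also in the paths between those constructs.
- It takes estimates from the same model: "This method will allow us to estimate the intervention effects on the constructs directly as well as their relationships to one another".
- It gives the standard for fit: "Well-fitting models will have fit indices of .90 or higher and <.06 for RMSEA".

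The only exploratory label nearby is in section 6.1: "In exploratory analyses, we will examine individual differences in response to treatment". That covers variation in response between individuals, not mediation.

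**The concern.** Lagrange Multiplier (LM) and Wald statistics come from fitting the model to data. If they help decide which paths enter or stay, and the same data then supply the p-values and estimates, the selected paths have been filtered for looking strong. A path admitted because it was significant will be significant again, and its size is biased away from zero. Deletion works the other way: a hypothesised path that fails its Wald test can be removed, and the evidence against the proposed mechanism is then missing from the final model.

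What is at stake is the Aim 2 claim about how the intervention works. Mechanism is part of the overall objective in section 2 and of the study purpose in the Data and Safety Monitoring Plan. The hypothesis is worded as one to be confirmed, while the procedure lets the model be revised before it is tested.

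**Working it through.** **Which data are used.** Section 8.2 names no second data set. The earlier pilot (section 1.2.2) cannot serve as one: all 101 participants were asked to use the tool, follow-up was 2 months, and HbA1c is not among its listed outcomes of interest. Use of the trial data for both steps is thus an inference, but the documents offer no alternative.

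**Inputs.** The plan states no sample size, power or error rate for Aim 2, so there is no figure of its own to reproduce. From section 10 I take 510 participants with outcome data (255 per arm) and alpha 0.05. The number of candidate paths, their independence, their true sizes and the 0.05 threshold for paths are my assumptions.

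**1. Chance of at least one false path.** With k independent null candidates this is 1 − 0.95^k.

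| k | Chance |
|---|---|
| 3 | 14% |
| 5 | 23% |
| 10 | 40% |
| 20 | 64% |

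In simulation (n = 510, five null paths and one true path, 4,000 runs per setting), selection at LM > 3.84 followed by a retest on the same data gave at least one false path in 22–23% of runs. A selected null path was significant on retest in 99.5–100% of cases. With selection on one half and testing on the other, that rate was 3.9–5.9%.

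**2. Inflation of selected paths.** The standard error of a standardised path is about 1/√510 = 0.0443. To be selected, an estimate must exceed 1.96 × 0.0443 = 0.087 in absolute value, so a true path of 0.05 cannot be both selected and estimated correctly.

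For a true path of 0.05:

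- The mean of z is 0.05/0.0443 = 1.13.
- The chance of selection is about 20%.
- The mean estimate given selection is about 0.11.

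Simulated means for selected paths:

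| True path | Mean if selected |
|---|---|
| 0.05 | 0.110 |
| 0.10 | 0.127 |
| 0.15 | 0.156 |
| 0.20 | 0.201 |
| 0.30 | 0.301 |

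The sample itself is unsettled, because the paragraph opens by restricting to those allocated to CareAvenue and later compares the arms. If only 255 were used, the selection threshold would be 1.96/√255 = 0.123, and weak paths would be inflated more.

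**3. The arm-difference test that the plan names.** This is a different event from step 1. I simulated a null path in two arms of 255 (20,000 runs) and tested the arm difference at 0.05.

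| Path selected | Rejection rate |
|---|---|
| No selection | 5.2% |
| On pooled arms | 5.5% |
| If significant in either arm | 33% |

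Section 8.2 does not say which form of selection applies.

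**The case against.** The wording is restrained. The tests are only considered, and changes are tied to the hypotheses and a conceptual model, so an automatic or unrestricted search is not described. Figure 1 is not reproduced in the text available to me, so the number of open paths is unknown. LM statistics within one model are generally correlated, so 1 − 0.95^k is illustrative. A mediation claim rests on an indirect effect, so one false path does not by itself create a false mechanism. All of this stands and limits how firmly any size can be stated. It does not remove the selection: a restriction to hypothesised paths narrows the candidates, but the tests still influence which of them survive.

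A reader might go further and infer that no Aim 2 p-value or path size is valid. The documents and the calculations do not support that. Paths fixed in advance and kept whatever the tests show are much less affected, paths of 0.20 or more show almost no bias, and the arm-difference test stays near 5% after pooled selection. A reader might also infer that paths will be altered until the fit cut-offs are met. Section 8.2 presents the indices as reporting guidance and states no such rule.

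**Conclusion.** The point holds in limited form. Followed as written, section 8.2 can admit false paths, overstate weak ones and lose hypothesised paths that fail, and nothing in the plan would show the reader that this had happened. Harm to the named arm-difference test runs from negligible (5.5%) to substantial (33%), depending on a choice the plan leaves open. These sizes rest on the assumed path counts, independence, effect sizes and 0.05 threshold, and on the inferred use of one data set. The primary HbA1c analysis is unaffected. This is a worthwhile and cheap improvement to Aim 2, not a threat to the trial's main result.

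**What to change.** State in section 8.2 that the Figure 1 model, with every path listed before unblinding, is the main Aim 2 analysis. Its direct and indirect effects are reported together with its fit indices, even if fit is poor. Report any model modified after LM or Wald tests alongside it, labelled exploratory, without confirmatory p-values, and list every path added or removed. The same edit should say which participants the model is fitted to, since the paragraph can be read two ways.

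This needs no new data and keeps the full sample. Splitting the data would also control the selection, but would leave about 255 participants in each half. The cost is a few sentences plus the path list, and more drafting if Figure 1 is not yet a complete model specification. The downside is that the main model may fit less well, and its estimates must be read with that in mind because a misspecified model can itself give biased effects.

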9 QUALITY CONTROL AND QUALITY ASSURANCE

The Data Manager in collaboration with the study PI and study biostatistician will be responsible for data quality assurance. The Data Manager will audit all data collected on a weekly basis to identify data discrepancies such as missingness, significant outliers, input errors, skip patterns errors, etc. All discrepancies will be documented and communicated to the PI on a weekly basis. The Data Manager will work with the PI to resolve discrepancies on a rolling basis throughout the study with resolutions being noted in the data discrepancy documentation. At the discretion of the PI, the study biostatistician will be consulted if there are data discrepancies that have the potential to significantly impact the study's primary or secondary outcomes.

10 STATISTICAL CONSIDERATIONS

The calculations used to determine study sample size for detecting differences between study arms at follow-up in our primary outcome of HbA1c are based on early data collected in the study. The hypothesis to be tested is that the intervention will lead to uptake of low-cost resources for health and unmet basic needs and reductions in CRN, thus leading to medication/regimen adherence and intensification. We expect the beneficial impacts from improved access to treatment recommendations and unmet basic needs can lead to improved HbA1c management and control. A 0.5 or greater reduction in HbA1c, after adjusting for

confounding covariates, is considered a clinically meaningful change in stabilizing or improving HbA1c control.⁵⁴ We designed the study to have 80% power at an alpha level of 0.05 to detect a change difference of 0.53 unit change in hemoglobin HbA1c between study arms, and a standard deviation of 1.46. This is based on early data collected in the study.⁵⁵ We will need a total of 510 participants (255 per arm) with outcome data to show a 0.53 unit difference in HbA1c. With this sample size, we will also have sufficient power to detect differences in our other self-reported secondary outcomes.

Intervention participants will be asked to give their provider their CareAvenue-generated action-plan to alert them of their needs and possibly receive additional support in accessing services. Although the intervention is targeted at the individual, physicians may change their behavior based on their interaction with treatment group patients and begin to better address unmet needs with control patients, thus raising the issue of contamination. That is, due to interactions with intervention patients, providers may alter “usual care.” This could diminish the effect size between intervention and control patients. One solution to this problem would be to conduct a cluster-randomized trial, which would obviate such contamination. We concluded, however, that because of the large number of unique providers seeing patients in the Diabetes Registry, the likelihood that a doctor will have patients in each arm is low. Further, some cross-over is inevitable because many patients in the Diabetes Registry see both a specialist and primary care provider, who may be randomized to different arms. Finally, a cluster randomized design would have required a large increase in sample size and cost. Although potential contamination lowers the treatment effect, we consider our design a strength of the study compared to a cluster randomized trial because baseline and follow-up assessments will allow us to quantify how much the control group also benefited from increased communication about low-cost treatment options with providers in the absence of the e-Health tool (comparing pre- and post- data among control patients within providers). This will demonstrate a generalized effect for the whole practice. We have increased the sample size by 3% to account for the potential that physicians’ behavior will spill over onto control patients. To account for a potential 12% loss to follow-up, we will recruit 600 participants. Based on our preliminary data from the pilot study and co-investigators’ prior studies with this population, we expect the following survey response rates: recruitment (72%), baseline (87%), follow-up 1 (94%), and follow-up 2 (80%).

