 - b. Non-serious UaPs will be reported within 14 calendar days.
3. All serious and non-serious UaPs will be reported to the DSMB within one week of reporting to the IRB.
4. Any action resulting in a temporary or permanent suspension of this study, such as actions by IRBMed, the study DSMB, or investigators, will be immediately reported to the appropriate NIDDK program official.

III. Safety Review Plan and Monitoring

Oversight of subject safety includes review of adverse events as well as study progress, data integrity and study outcomes.

A. Justification of sample size

We propose to enroll 600 subjects in this study. The hypothesis to be tested is that the intervention will lead to uptake of low-cost resources for health and unmet basic needs and reductions in CRN, thus leading to medication/regimen adherence and intensification. We expect the beneficial impacts from improved access to treatment recommendations and unmet basic needs can lead to improved HbA1c

management and control. A 0.5 or greater reduction in HbA1c, after adjusting for confounding covariates, is considered a clinically meaningful change in stabilizing or improving HbA1c control.¹ We designed the study to have 80% power at an alpha level of 0.05 to detect a change difference of 0.53 unit change in hemoglobin HbA1c between study arms, and a standard deviation of 1.46 based on early data collected in the study.² We will need a total of 510 subjects (255 per arm) with outcome data to show a 0.53 unit difference in HbA1c. With this sample size, we will also have sufficient power to detect differences in our other self-reported secondary outcomes.

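### The stated inputs (difference 0.53, SD 1.46, 80% power, alpha 0.05) require about 240 participants with outcome data, not the stated 510

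*Combined protocol and SAP*

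**What the plan says.** Section 10 (Statistical Considerations) introduces the calculation as one for "detecting differences between study arms at follow-up in our primary outcome of HbA1c". It gives the operating characteristics, "We designed the study to have 80% power at an alpha level of 0.05", and the effect and spread: "to detect a change difference of 0.53 unit change in hemoglobin HbA1c between study arms, and a standard deviation of 1.46". The result follows: "We will need a total of 510 participants (255 per arm) with outcome data to show a 0.53 unit difference in HbA1c".

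Two allowances come later in the same section. For contamination of control patients through their physicians: "We have increased the sample size by 3% to account for the potential". For attrition: "To account for a potential 12% loss to follow-up, we will recruit 600 participants".

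Appendix 4 (Data Safety Monitoring Plan), III.A, repeats the inputs and the result: "We will need a total of 510 subjects (255 per arm) with outcome data to show a 0.53 unit difference in HbA1c".

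The primary analysis in section 8.2 is a mixed model in which "the coefficient of the treatment-by-time period interaction effect estimates the key parameter of interest: changes in HbA1c levels".

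The plan does not give the sidedness of the test, the formula, a baseline/follow-up correlation, a design effect or a multiplicity adjustment. It does not say whether 1.46 is the SD of change or of HbA1c at one visit. It says that the inputs come from early data collected in the study, which are not shown.

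**The concern.** The four inputs are complete for a comparison of two means, so the reader can check the answer, and it does not come out. The standardised difference is 0.53 / 1.46 = 0.36. At 80% power that calls for well under 255 per arm.

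This is the only sample-size justification in the documents, and it is carried into the monitoring plan. Section 10 treats a reduction of 0.5 or more as clinically meaningful, so power at 0.5 determines how a null result should be read. A null result with 97% power is strong evidence against an effect of that size. With about 75% power it is not. The DSMB charter also allows termination when a significant difference is improbable, and that judgement needs a dependable SD and effect size. As printed, the text supports neither.

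**Working it through.** **Inputs.** From section 10: difference d = 0.53, SD = 1.46, power 80%, alpha 0.05, equal arms, 255 per arm with outcome data. Two-sided testing is my assumption, because the Aim 1 hypothesis in section 2 is non-directional.

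**Step 1. Try to reproduce 255 per arm.** The normal approximation is n per arm = 2 × [(z₀.₉₇₅ + z₀.₈₀) × SD / d]².

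2 × [(1.960 + 0.842) × 1.46 / 0.53]² = 119.1.

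The t-test version gives 120.1 per arm, about 240 in total. The ratio 510 / 240 is 2.1. The stated figure is not reproduced.

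**Step 2. Other settings with SD 1.46.**

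| Variation | n per arm |
|---|---|
| One-sided, 80% power | 94.5 |
| Two-sided, 90% power | about 160 |
| Two-sided, 95% power | about 198 |

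None reaches 255, and the text states 80% power.

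**Step 3. The allowances.** The figure of 510 is defined as participants with outcome data, so attrition is applied after it. 510 × 1.03 / 0.88 = 597, which rounds to 600. Both allowances therefore appear to sit after 510. If 510 already contained the 3%, the base would be 510 / 1.03 = 495, still about twice 240.

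**Step 4. Read 1.46 as a single-visit SD with change as the endpoint.** Then SD of change = 1.46 × √[2(1 − ρ)], where ρ is the baseline/follow-up correlation. No ρ is given, so the table shows a range. Power is at 255 per arm, two-sided t-test.

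| ρ | SD of change | n per arm for 0.53 | Power for 0.53 | Power for 0.5 |
|---|---|---|---|---|
| 0 | 2.065 | 239.2 | 82.5% | 77.9% |
| 0.3 | 1.727 | 167.7 | 93.3% | 90.4% |
| 0.5 | 1.46 | 120.1 | 98.3% | 97.1% |

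Zero correlation gives about 480 in total, still short of 510, and any positive correlation needs fewer. Reaching 255 per arm this way requires ρ of about −0.07, which is implausible for repeated HbA1c in the same person.

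**Step 5. What 255 per arm delivers if 1.46 is the SD of change.** Power is 98.3% for 0.53 and 97.1% for 0.5. The difference detectable with 80% power is 0.36.

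**Step 6. What SD would give 255.** Solving backwards, 80% power for 0.53 at 255 per arm implies an SD of about 2.13. That equals 1.46² = 2.1316. Entering 2.1316 as the SD gives 254.9 per arm and 80.0% power, which matches the printed figure. A variance entered where an SD was required would produce exactly this, but the documents do not confirm it. If the true SD were 2.13, power for 0.5 would be 75.3%.

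**The case against.** The best defence is that 240 rests on one reading of 1.46. Section 10 speaks both of a difference at follow-up and of a difference in change, and section 8.2 tests change. If 1.46 is a single-visit SD and the planners conservatively took zero correlation, about 480 are needed. The excess is then about 6%, not a factor of 2.1.

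The defence can go further. Section 10 describes contamination as shrinking the effect. Cutting the effect by 3%, to 0.53 × 0.97 = 0.514, with a single-visit SD and zero correlation gives 254.2 per arm, which rounds up to 255. So the variance-for-SD explanation is not the only route to the printed number.

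Some of this stands. The cause is not established, the meaning of 1.46 is open, and the variance explanation should be treated only as something to check. The second route is nonetheless weak. It needs a zero correlation stated nowhere. It also turns the 3% into a cut in the effect, which raises N by about 6% (1 / 0.97² = 1.063), whereas the text says that the sample size itself was raised by 3%. And it uses the contamination allowance before 510, although 600 is recovered only with the 3% applied after it: 510 / 0.88 alone is 580.

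It is also fair to say that the practical consequence is limited. On the SD as printed, the error is conservative or close to neutral for 0.53, and the paragraph in the monitoring plan is a copy, not a second error.

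**Conclusion.** The concern holds. On the inputs as written, with a two-sided test and 1.46 as the SD of the quantity compared, 240 participants with outcome data are enough, and 510 is overstated by a factor of 2.1. On the least favourable reading (single-visit SD, change endpoint, zero correlation) the requirement is about 480, so 510 still does not follow from what is stated.

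No shortfall against the 80% target for 0.53 is shown. Power for 0.53 at 255 per arm runs from 82.5% to 98.3% across correlations of 0 to 0.5, and is 80.0% if the true SD is 2.13. What is lost is a usable statement of power at 0.5: 97% if 1.46 is the SD of change, 78% if it is a single-visit SD with zero correlation, and 75% if the SD is really 2.13. The figure should be corrected. That 510 is not reproducible is certain. Why it is wrong cannot be settled from the documents.

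**What to change.** Leave enrolment at 600. Retrieve the original calculation and establish four things: the formula and sidedness; whether 1.46 is the SD of change or of one visit; whether 1.46² was entered as the SD; and whether 510 already contains the 3%. Then revise section 10 and Appendix 4, III.A, together.

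- **If 1.46 is the SD of change:** state that 510 participants with outcome data (255 per arm) give about 98% power for 0.53, 97% for 0.5, and 80% power at about 0.36, with two-sided alpha 0.05.
- **If 1.46 is a single-visit SD:** state the assumed baseline/follow-up correlation and the resulting power, which is about 82% for 0.53 at zero correlation and higher with positive correlation.
- **If the source data show that 2.13 is truly the SD:** print it, and state also that power for 0.5 is about 75%. Do not print it otherwise.

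The cost is one look-up and two paragraphs of wording. Enrolment, endpoints and analysis do not change.
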